### 8.3.9 REPORTING OF PREGNANCY

Pregnant patients or those planning to become pregnant will be excluded from study participation. If a patient enrolled becomes pregnant anytime during the follow-up period then the study drug will be stopped and the patient will be discontinued from the study. The IRB will not be notified unless the patient meets reporting criteria from experiencing a serious adverse event.

## 8.4 UNANTICIPATED PROBLEMS

### 8.4.1 DEFINITION OF UNANTICIPATED PROBLEMS (UP)

The Office for Human Research Protections (OHRP) considers unanticipated problems involving risks to participants or others to include, in general, any incident, experience, or outcome that meets all of the following criteria:

- Unexpected in terms of nature, severity, or frequency given (a) the research procedures that are described in the protocol-related documents, such as the Institutional Review Board (IRB)-approved research protocol and informed consent document; and (b) the characteristics of the participant population being studied;
- Related or possibly related to participation in the research (“possibly related” means there is a reasonable possibility that the incident, experience, or outcome may have been caused by the procedures involved in the research); and
- Suggests that the research places participants or others at a greater risk of harm (including physical, psychological, economic, or social harm) than was previously known or recognized.

#### 8.4.2 UNANTICIPATED PROBLEM REPORTING

The investigator will report unanticipated problems (UPs) to the reviewing Institutional Review Board (IRB) and to the lead principal investigator (PI). The UP report will include the following information:

- Protocol identifying information: protocol title and number, PI's name, and the IRB project number;
- A detailed description of the event, incident, experience, or outcome;
- An explanation of the basis for determining that the event, incident, experience, or outcome represents an UP;
- A description of any changes to the protocol or other corrective actions that have been taken or are proposed in response to the UP.

To satisfy the requirement for prompt reporting, UPs will be reported using the following timeline:

- UPs that are serious adverse events (SAEs) will be reported to the IRB within 5 business days and to the primary investigator and Independent Safety Monitor within 24 hours of the investigator becoming aware of the event.
- Any other UP will be reported to the IRB and primary investigator within 5 business days of the investigator becoming aware of the problem.
- All UPs should be reported to appropriate institutional officials (as required by an institution's written reporting procedures), the supporting agency head (or designee), and the Office for Human Research Protections (OHRP) within 48 hours of the IRB's receipt of the report of the problem from the investigator.

#### 8.4.3 REPORTING UNANTICIPATED PROBLEMS TO PARTICIPANTS

Patients will not be informed of unanticipated problems apart from those self-reported by them during primary and secondary endpoint data collection, or those necessitating premature termination or suspension of the study as a whole.

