## STATEMENT OF COMPLIANCE

This trial will be conducted in accordance with the International Conference on Harmonization Good Clinical Practice (ICH GCP), applicable United States (US) Code of Federal Regulations (CFR), and the University of Missouri School of Medicine Terms and Conditions of Award. The Principal Investigator will assure that no deviation from, or changes to the protocol will take place without prior agreement from the Investigational New Drug (IND) or Investigational Device Exemption (IDE) sponsor, funding agency and documented approval from the Institutional Review Board (IRB), except where necessary to eliminate an immediate hazard(s) to the trial participants. All personnel involved in the conduct of this study have completed Human Subjects Protection and ICH GCP Training.

The protocol, informed consent form(s), recruitment materials, and all participant materials will be submitted to the IRB for review and approval. Approval of both the protocol and the consent form must be obtained before any participant is enrolled. Any amendment to the protocol will require review and approval by the IRB before the changes are implemented to the study. All changes to the consent form will be IRB approved; a determination will be made regarding whether a new consent form needs to be obtained from participants who provided consent, using a previously approved consent form.

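### Section 8.4.3 bars telling current participants of unanticipated problems that raise their risk if the study continues

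*Combined protocol and SAP*

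**What the plan says.** Section 8.4.1 lists three criteria for an unanticipated problem and requires all of them to be met. The third is that it "Suggests that the research places participants or others at a greater risk of harm" than was known before.

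Section 8.4.2 says who is told. Problems that are serious adverse events "will be reported to the IRB within 5 business days and to the primary investigator and Independent Safety Monitor within 24 hours". For the rest, "Any other UP will be reported to the IRB and primary investigator within 5 business days". Institutional officials, the head of the supporting agency and OHRP are also notified. Participants are not on the list. The report must include "A description of any changes to the protocol or other corrective actions", whether already taken or only proposed.

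Section 8.4.3 then deals with participants directly: "Patients will not be informed of unanticipated problems apart from those self-reported by them during primary and secondary endpoint data collection". It adds one further exception, for problems serious enough to halt the trial, whether for good or for a time.

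**The concern.** The definition and the disclosure rule work against each other. Something is an unanticipated problem only if it suggests more risk than participants were told of when they consented, yet the default in 8.4.3 is silence. The self-report exception reaches only the person who already knows of the event. The other exception needs the whole study to be stopped or suspended. Between the two lies a problem that raises risk while the trial goes on. There the IRB and the investigator are informed, and the people taking capsules are not.

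What is at stake is a participant's ability to decide, on current information, whether to keep taking the product or to withdraw. Section 2.3.3 acknowledges that the combination has not been evaluated in the proposed manner, so unforeseen risk cannot be ruled out. This is a point of participant protection. It does not touch the endpoints, the sample size or the validity of the analysis.

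**Working it through.** The main check is textual: does any other visible section require disclosure when the study continues?

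| Section | What it provides | Does it fill the gap? |
|---|---|---|
| 8.4.2 | Corrective actions must be described in the report | No. Telling participants could be one of them, but is not required |
| 10.1.1.2 | Consent is a process that continues during participation | No. It is a general statement with no stated duty to pass on new risks |
| Statement of Compliance, consent | When the form changes, "a determination will be made regarding whether a new consent form needs to be obtained from participants who provided consent" | Only in part. It depends on a form revision, is decided case by case and is not tied to unanticipated problems |
| Statement of Compliance, deviations | No departure from the protocol without prior agreement and IRB approval, "except where necessary to eliminate an immediate hazard(s) to the trial participants" | Only for immediate hazards. For a lesser rise in risk, an investigator who wished to tell participants would be departing from 8.4.3 |
| 10.1.2 | Participants are promptly informed if the study is suspended or terminated | Only if that step is taken. 8.4.3 already excepts it |

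What remains is a problem that raises risk, is not an immediate hazard and is not judged to warrant even temporary suspension.

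**How many people at once.** The plan gives no figure for this, so there is none to reproduce. The inputs are:

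- participation of 8 days including enrollment day (1.1)
- a five-day course (6.1.2)
- study window May 30, 2022 to June 1, 2023, which is 367 days (1.1)
- target of 100, randomized 1:1 (4.1, 9.2)
- planned accrual of 5 to 10 per week (5.5)

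The pace that would just reach the target in the window is 100 / 367 × 7 = 1.9 per week. This is an assumption. The actual pace is not given, and the summary of changes says only that enrollment was slower than anticipated.

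With steady accrual, the mean number present is the weekly rate / 7 × the days present:

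| Enrolled per week | In participation (× 8 days) | In the five-day course (× 5 days) | Of those, on active product (half) |
|---|---|---|---|
| 1.9 | 2.2 | 1.4 | 0.7 |
| 5 | 5.7 | 3.6 | 1.8 |
| 10 | 11.4 | 7.1 | 3.6 |

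These counts cover the randomized trial only. The ten blood-sampling participants are separate.

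**The case against.** Several points on the other side narrow the concern, and most of them stand.

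**Suspension is a broad route.** Section 10.1.2 lists unexpected, significant or unacceptable risk as grounds that may warrant temporary suspension, and any one is enough. Many unanticipated problems could qualify, and participants would then be told. Sections 4.4 and 8.3.5 also let the IRB, the safety monitor or the investigators end the study at any time. This shrinks the gap but does not close it, because suspension is permitted and not required.

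**The consent form may cover it.** Section 10.1.1.1 says the consent form for the randomized trial is provided separately. It may contain a new-information clause. If it does, participants are better protected than 8.4.3 suggests, but the protocol and the form then disagree and 8.4.3 still needs correcting.

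**Few people and a short exposure.** This is true. The table gives small numbers, and half of those in the course are on placebo.

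A reader might also infer three stronger things that the documents do not support.

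- *That reporting always comes too late for current participants.* The five-business-day limit for the IRB is a maximum. Serious events reach the primary investigator and the safety monitor within 24 hours, and 8.4.2 allows for corrective action already taken when the report is made.
- *That new enrollees must be kept uninformed.* Section 8.4.3 does not restrict what the consent form may say.
- *That 8.3.7 bars participants from learning their own study-detected results.* Its second sentence provides for incidental findings from enrollment to be telephoned to patients. Sections 8.1 and 8.2 require patients whose study-related test results meet an exclusion criterion to be told to stop the product, and 7.1 calls for a management decision on significant findings. The wording of 8.3.7 could be clearer, but it is not a clear bar.

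**Conclusion.** The concern holds in a limited form. As written, 8.4.3 forbids telling other current participants of a newly recognised rise in risk whenever the study continues and the hazard is not immediate. No visible section imposes the opposite duty. It should be fixed, because the text is an express prohibition and not merely an omission.

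It affects on average about 2 people at a time at 1.9 enrolled per week, and about 6 to 11 at the planned pace. If accrual was slower than 1.9 per week, the number is below 2. The documents give no rate of unanticipated problems, so how often the rule would operate cannot be estimated.

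The conclusion rests on reading 8.4.3 literally and on the visible protocol alone. It would be inferring too much to say that participants would in fact have been left uninformed: the consent form may promise otherwise, and the investigators may suspend the study.

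**What to change.** Replace 8.4.3 with a rule of this kind. When the primary investigator determines that an event is an unanticipated problem bearing on participants' risk, all current participants are told promptly, for example at their next daily telephone visit, even if the study continues. The same message goes to both arms and does not reveal treatment assignment. The consent form is updated for new enrollees. The limit to participants' own risk is needed because 8.4.1 also covers problems that affect only others.

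Participants in the blood-sampling study have no daily calls, so they would need a separate call.

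The cost is a short amendment with IRB approval. For randomized participants the channel already exists, since 6.3 and 8.1 provide for seven consecutive daily calls. The added work is occasional extra content in those calls. Endpoints, sample size and planned analyses stay as they are.

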### 9 STATISTICAL CONSIDERATIONS

#### 9.1 STATISTICAL HYPOTHESES

- Primary Efficacy Endpoint(s):
  1. Combination supplementation with zinc, green tea extract, and ascorbic acid is associated with a decrease in duration and severity of cold and flu-like symptoms following five days of treatment as compared to placebo (superiority analysis). Analysis will be conducted following seven days of follow-up.
- Secondary Efficacy Endpoint(s):

1. Rates of adverse events including, nausea, vomiting, indigestion, worsening of shortness of breath or difficulty breathing, allergic reaction (skin rash, hives, swelling of lips or tongue), and hospitalized or physician visit for study drug related adverse effect will not occur more frequently with combination supplementation with zinc, green tea extract, and ascorbic acid as compared to placebo (superiority analysis). Analysis will be conducted following seven days of follow-up.
2. Rates of patient-reported days missed from work or school and hospitalization or physician office visit(s) for respiratory viral illness related complications will occur less frequently with combination supplementation with zinc, green tea extract, and ascorbic acid as compared to placebo (superiority analysis). Analysis will be conducted following seven days of follow-up.

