## 9.2 SAMPLE SIZE DETERMINATION

The target number of subjects to be enrolled during the study period occurring May 2022 – June 2023 is 100 (50 patients randomized to placebo and 50 to the supplementation group). This target is derived from a similarly conducted study evaluating zinc supplementation (without green tea extract) in a comparable adult population as identified with the current proposal. Based on an assumption that 60% of patients taking study drug and 30% in the placebo group would recover from cold and flu-like symptoms after five days of treatment a total of 84 patients would be sufficient to reach 80% power with a two tailed p value <0.05 to detect differences between groups. The power calculation was

$$N_1 = \left\{ z_{1-\alpha/2} * \sqrt{\bar{p} * \bar{q} * (1 + \frac{1}{k})} + z_{1-\beta} * \sqrt{p_1 * q_1 + (\frac{p_2 * q_2}{k})} \right\}^2 / \Delta^2$$

$$q_1 = 1 - p_1$$

$$q_2 = 1 - p_2$$

$$\bar{p} = \frac{p_1 + kp_2}{1 + K}$$

$$\bar{q} = 1 - \bar{p}$$

$$N_1 = \left\{ 1.96 * \sqrt{0.45 * 0.55 * (1 + \frac{1}{1})} + 0.84 * \sqrt{0.3 * 0.7 + (\frac{0.6 * 0.4}{1})} \right\}^2 / 0.3^2$$

$$N_1 = 42$$

$$N_2 = K * N_1 = 42$$

$p_1, p_2$  = proportion (incidence) of groups #1 and #2  
 $\Delta = |p_2 - p_1|$  = absolute difference between two proportions  
 $n_1$  = sample size for group #1  
 $n_2$  = sample size for group #2  
 $\alpha$  = probability of type I error (usually 0.05)  
 $\beta$  = probability of type II error (usually 0.2)  
 $z$  = critical Z value for a given  $\alpha$  or  $\beta$   
 $K$  = ratio of sample size for group #2 to group #1

performed using an online tool located at <https://clincalc.com/stats/samplesize.aspx> with the following calculations performed:

The anticipated dropout rate is 5% based on a large randomized control study evaluating safety of EGCG following 12 months of treatment using a similar daily dosage as the current proposal. No interim analysis is planned; power calculation is for primary endpoint only.

The primary outcome will be compared using the Chi-square test. Secondary outcomes will be assessed using the Chi-square test for categorical data and student's t-test for continuous data. An exploratory analysis comparing the primary outcome among COVID-19 only patients will also be conducted. All inferential testing will be based on intention-to-treat.

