### 9.4 STATISTICAL ANALYSES

#### 9.4.1 GENERAL APPROACH

Descriptive statistics for continues data will be expressed at means with standard deviations and categorical data will be expressed as percentage of total cohort. Inferential testing will use two-tailed p value <0.05 with 95% confidence intervals to determine statistical significance.

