#### 9.4.2 ANALYSIS OF THE PRIMARY EFFICACY ENDPOINT(S)

The primary endpoint will be determined from observing the proportion of patients (expressed as percentage) recovered from cold and flu-like symptoms (defined as scoring 0 or 1 daily total symptom severity score) following seven days of follow-up. Recovery from cold and flu-like symptoms will be categorically assessed as a single endpoint. The difference in recovery rates between study drug and placebo will be compared using Chi-squared test and be expressed with 95% confidence intervals. Analysis will be performed based on intention-to-treat. Missing data will be handled by last observation carried forward based on most recent self-reported total daily symptom severity score.

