#### 9.4.3 ANALYSIS OF THE SECONDARY ENDPOINT(S)

Secondary endpoints are independent of findings from the primary endpoint.

Rates of adverse events will be determined as a percentage of those subjects self-reporting an event compared to the total cohort following seven days of follow-up. Adverse events will be categorically expressed as a single endpoint. Difference in adverse events will be compared using Chi-squared test with incidence rates expressed as percentages. Analysis will be performed based on intention-to-treat. Missing data will be handled by last observation carried forward based on most recent self-reported adverse event (or lack thereof).

Rates of missed days of work or school will be determined as a percentage of those subjects self-reporting a missed day compared to the total cohort following seven days of follow-up. Missed days will be both categorically expressed as a single endpoint with incidence rates expressed as percentages as well as mean days missed with standard deviation. Difference in missed days will be compared using Chi-squared test for categorically expressed missed days (occurrence of any missed day(s) during study follow-up) and student's t-test for mean days missed. Analysis will be performed based on intention-to-treat. Missing data will be handled by last observation carried forward based on most recent self-reported missed day (or lack thereof).

Rates of seeking medical care including physician office visits or hospitalization for worsening respiratory illness will be determined as a percentage of those subjects self-reporting these events compared to the total cohort following seven days of follow-up. A physician office visit or hospitalization for worsening respiratory illness will be categorically expressed as a single endpoint with incidence rates expressed as percentages. Difference in need to seek medical care will be compared using Chi-squared tests. Analysis will be performed based on intention-to-treat. Missing data will be handled by last observation carried forward based on most recent self-reported medical visit (or lack thereof).

---

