#### 9.4.4 SAFETY ANALYSES

Rates of adverse events including, nausea, vomiting, indigestion, worsening of shortness of breath or difficulty breathing, allergic reaction (skin rash, hives, swelling of lips or tongue), and hospitalized or physician visit will be included in secondary analysis as outlined in **Section 9.4.3**. Unsolicited adverse events recorded will be categorized as “other adverse events” and will be described as a incidence rate expressed as a percentage. Each adverse event recorded will be only counted once for any given study subject during the study follow-up period. The 10th revision of the International Statistical Classification of Diseases and Related Health Problems (ICD-10) codes will be used to code adverse events where appropriate. Severity of adverse events will be classified as follows:

- **MILD:** Awareness of signs or symptoms, but easily tolerated and are of minor irritant type causing no loss of time from normal activities. Symptoms do not require therapy or a medical evaluation; signs and symptoms are transient.
- **MODERATE:** Events introduce a low level of inconvenience or concern to the participant and may interfere with daily activities, but are usually improved by simple therapeutic measures; moderate experiences may cause some interference with functioning
- **SEVERE:** Events interrupt the participant's normal daily activities and generally require systemic drug therapy or other treatment; they are usually incapacitating

Expectedness of adverse events will be determined as follows:

- **UNEXPECTED** - nature or severity of the event is not consistent with information about the condition under study or intervention in the protocol, consent form, product brochure, or investigator brochure.
- **EXPECTED** - event is known to be associated with the intervention or condition under study.

Relatedness of adverse events will be determined as follows:

- DEFINITELY RELATED: The adverse event is clearly related to the investigational agent/procedure – i.e. an event that follows a reasonable temporal sequence from administration of the study intervention, follows a known or expected response pattern to the suspected intervention, that is confirmed by improvement on stopping and reappearance of the event on repeated exposure and that could not be reasonably explained by the known characteristics of the subject's clinical state.

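### Section 9.1 makes a no-excess claim for adverse events and labels it superiority, and the planned two-sided chi-square has no margin or confidence-limit rule that could support it

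*Combined protocol and SAP*

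**What the plan says.** Section 9.1 lists adverse events under its secondary efficacy hypotheses and states that their rates "will not occur more frequently with combination supplementation with zinc, green tea extract, and ascorbic acid as compared to placebo (superiority analysis". The next hypothesis in that list, on missed days and medical visits, predicts fewer events on the supplement and carries the same label, which fits there.

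The analysis is set out in four places:

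- Section 9.2: "Secondary outcomes will be assessed using the Chi-square test for categorical data". It adds that the "power calculation is for primary endpoint only".
- Section 9.4.1: "Inferential testing will use two-tailed p value <0.05 with 95% confidence intervals to determine statistical significance".
- Section 9.4.3: "Adverse events will be categorically expressed as a single endpoint", and "Difference in adverse events will be compared using Chi-squared test with incidence rates expressed as percentages".
- Section 9.4.4 refers back to 9.4.3 for the solicited events and adds: "Each adverse event recorded will be only counted once for any given study subject during the study follow-up period".

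No section states a margin, or a confidence limit that would allow the conclusion that events are not more frequent.

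**The concern.** The hypothesis and the test do not match. A two-sided chi-square test asks whether the arms differ. It can show an excess or a reduction, but failing to show either is not evidence that there is no excess. The only valid route to the 9.1 hypothesis is therefore a significant reduction. That is a stronger claim than the text makes, and an unlikely result given that Section 2.3.3 expects an additive nausea risk. (The same section anticipates that dosing after meals will lessen gastrointestinal upset, so this is a tension and not a contradiction for every event.)

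The tested variable is also unclear. The single endpoint in 9.4.3 most likely means any adverse event, pooled. But 9.4.2 uses the same phrase for recovery ("Recovery from cold and flu-like symptoms will be categorically assessed as a single endpoint"), where it means one yes/no per participant, so it could mean that for each event type instead. If events are pooled, those the illness itself can cause, such as worsening shortness of breath, would dilute a treatment difference.

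Comparing adverse events is the first secondary objective. A sizeable excess could give p > 0.05, and nothing in the plan prevents that from being reported as support for the hypothesis.

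**Working it through.** **Inputs.** 50 per arm (Sections 4.1 and 9.2); two-sided 0.05 (9.4.1); chi-square (9.2, 9.4.3). Rates cited in Section 2.3.1: nausea 10.2% vs 4.8% (EGCG vs placebo); nausea and stomach distress 13.5% vs 10.7% (zinc vs placebo). The documents give no adverse event margin and no pooled adverse event rate.

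**The plan's own figure.** Section 9.2, 60% vs 30% recovery:

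N per arm = [1.96 × √(0.45 × 0.55 × 2) + 0.84 × √(0.21 + 0.24)]² / 0.3² = (1.379 + 0.563)² / 0.09 = 41.9, so 42 per arm and 84 in total. It reproduces, but concerns recovery only.

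**1. How large an excess stays non-significant?** With a and b events of 50 and pooled proportion p̄ = (a + b)/100, the Pearson statistic without continuity correction is

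χ² = ((a − b)/50)² / [p̄(1 − p̄) × 2/50], compared with 3.84.

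For 12 vs 5: p̄ = 0.17, so χ² = 0.0196 / (0.17 × 0.83 × 0.04) = 0.0196 / 0.005644 = 3.47, p = 0.062.

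| Placebo events | Largest non-significant active count | Excess (points) | χ² | p |
|---|---|---|---|---|
| 2 | 7 | 10 | 3.05 | 0.081 |
| 5 | 12 | 14 | 3.47 | 0.062 |
| 10 | 18 | 16 | 3.17 | 0.075 |
| 11 | 20 | 18 | 3.79 | 0.052 |
| 15 | 24 | 18 | 3.41 | 0.065 |
| 20 | 29 | 18 | 3.24 | 0.072 |

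The gap is 9 participants for every placebo count from 11 to 30.

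**2. What do such results leave open?** Newcombe 95% interval from Wilson limits (l, u), with d = p₁ − p₂:

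lower = d − √[(p₁ − l₁)² + (u₂ − p₂)²]; upper = d + √[(u₁ − p₁)² + (p₂ − l₂)²].

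For 12/50 vs 5/50 the Wilson limits are 0.143 to 0.374 and 0.043 to 0.214, giving −0.9 to +28.6 points. For 24/50 vs 15/50 the interval is −1.1 to +35.3 points. Even identical counts of 5/50 leave an upper limit of +12.7 points.

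**3. Can a significant reduction be expected?** With 3 placebo events, even 0 active events is not significant (χ² = 3.09, p = 0.079); 0 vs 4 is the first that is (p = 0.041). If the true rates were equal, the probability of a significant reduction is 2.1% at 4.8% and 2.6% at 10.7% (full binomial enumeration).

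**4. Power to see an excess (illustration only).** This assumes the cited single-component rates apply here. The last two rows also assume that the two cited excesses add: 5.4 + 2.8 = 8.2 points.

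| Active vs placebo | Exact two-sided power |
|---|---|
| 10.2% vs 4.8% | 16.2% |
| 13.5% vs 10.7% | 7.5% |
| 13.0% vs 4.8% | 29.7% |
| 18.9% vs 10.7% | 22.2% |

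Even with the excesses added, p > 0.05 occurs in about 70% to 78% of trials.

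**5. Would a margin rescue the claim at 50 per arm?** Probability that the Newcombe 95% upper limit falls below the margin when there is no true excess. The margins and the 20% rate are illustrative.

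| Event rate in both arms | 10-point margin | 15-point margin |
|---|---|---|
| 4.8% | 52% | 83% |
| 10.7% | 32% | 62% |
| 20% | 23% | 47% |

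**The case against.** The strongest reply is that only one sentence in 9.1 makes a no-excess claim. The objective in Sections 1.1 and 3 is simply to compare adverse events, and no section says that p > 0.05 will be taken as evidence of equal frequency. Section 9.4.1 attaches 95% confidence intervals to inferential testing in general, 9.4.8 tabulates data by measure, and 9.2 is open that only the primary endpoint is powered. Safety during the trial rests on the Independent Safety Monitor (Sections 8.3.5, 10.1.6 and 10.1.7). The power figures use nausea rates for single components from other settings, one of them a 12-month trial, while the tested variable is probably pooled adverse events.

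Much of this stands. The harm is conditional and lies in the conclusion drawn at the final analysis; participant protection does not depend on it. Low power for a secondary safety comparison in a 100-patient phase 2 trial is not itself a defect. The power figures are illustrations, but the count results in steps 1 and 2 need no assumed rate. The neutral objective makes 9.1 easier to correct but does not remove the mismatch. The intervals in 9.4.1 serve to judge significance against zero, and while 9.4.2 asks explicitly for an interval on the recovery difference, 9.4.3 asks only for percentages for adverse events.

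**Conclusion.** The concern holds. As written, the planned analysis cannot validly support the 9.1 adverse event hypothesis except through a significant reduction, which the hypothesis does not claim. With 50 analysed per arm and an uncorrected chi-square, excesses of 10 to 18 percentage points over the placebo counts tabulated above are compatible with p > 0.05, and the upper confidence limits in the two worked examples are about 29 and 35 points. Those figures follow from the design alone. The power and margin figures rest on assumed event rates and show only the order of magnitude. This should be corrected before the final analysis, because it affects a named secondary objective. The primary result is not threatened.

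**What to change.** - **Section 9.1:** remove the superiority label from the adverse event item and replace the hypothesis with an estimation aim, for example: *to estimate the difference between arms in the percentage of participants reporting each solicited adverse event, and any adverse event, over seven days.* This brings 9.1 into line with the objective in Section 3.
- **Sections 9.4.3 and 9.4.4:** state whether the single endpoint means any adverse event. Report each solicited event and any event by arm, with the risk difference and a 95% confidence interval from a method suited to small counts (Newcombe is one choice). State that p > 0.05 will not be used to conclude that there is no excess.

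The alternative is to keep the claim with a justified, prespecified margin and an upper-limit rule. As the last table shows, that is weak at 50 per arm.

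The cost is wording only. Each solicited event is already asked about daily (Section 8.2) and counted once per participant (9.4.4), so no new data are needed. Sample size and primary analysis are unchanged. The sponsor gives up a claim of no more adverse events than placebo.
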